## SECTION K - WORK PLACE EXPOSURES

K1. Do you work where you are exposed to human bodily fluids (e.g. blood, urine, feces, saliva)?  
(Choose one)

0 No ***Skip to Section L if Study group 1 (A7=1), Skip to Question L9 if Study group 2 (A7=2), Else Skip to Instruction After L9.***

1 Yes

97 Don't Know

98 Refuse to Answer

K2. In the 6 months before your donation, in your professional work have you had a needle stick injury (accidentally been stuck by a needle or other sharp instrument used for providing medical care to someone else)? (Choose one)

0 No

1 Yes

97 Don't Know

98 Refuse to Answer

K3. In the 6 months before your donation, did you in your professional work have someone else's blood, body fluids, or excrement splashed into your eyes, mouth or in an open skin lesion? (Choose one)

0 No

1 Yes

97 Don't Know

98 Refuse to Answer

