- 6 A gel used as part of a research study
- 7 Other (please specify); \_\_\_\_\_

J18a. In the 6 months before your donation, have you had Raatib, ritual scarring, ritual piercing, ritual circumcision, blood sharing or been stabbed?

- |    |                  |                    |
|----|------------------|--------------------|
| 0  | No               | Skip to J20 |
| 1  | Yes              |                    |
| 97 | Don't Know       |                    |
| 98 | Refuse to Answer |                    |

J18b. Can you please tell us which activity? (Check all that apply)

- 1 Raatib
- 2 Ritual scarring
- 3 Ritual piercing
- 4 Ritual circumcision
- 5 Blood sharing
- 6 Been stabbed
- 7 Other (please specify); \_\_\_\_\_

J19. What was the reason for the activity?

- 1 Cultural, ritual, religious
- 2 Administering a substance in my skin for treatment or prevention
- 3 Letting out blood
- 4 Sealing a "blood pact"
- 5 Other

97 Don't Know

98 Refuse to Answer

J20. In the 6 months before your donation, did you visit a traditional healer and receive traditional medicine other than cuts and/or scarification?

0 No

1 Yes

97 Don't Know

98 Refuse to Answer

J21. In the 6 months before your donation, did you live in an environment where you were frequently bitten by mosquitos?

0 No

1 Yes

97 Don't Know

98 Refuse to Answer

J22. In the 6 months prior to your last donation, did you live in an environment where you were frequently bitten by bed bugs or lice?

- 0 No
- 1 Yes
- 97 Don't Know
- 98 Refuse to Answer

J23. In the 6 months prior to your last donation, did you have an injury such as a knife or stab wound or were you in an accident where you lost blood from a cut or injury?

- 0 No
- 1 Yes
- 97 Don't Know
- 98 Refuse to Answer

**READ and HEARD:** Now, we would like to know about any personal contact you have had with persons who have HIV or hepatitis. In each question, please include only family members, personal friends or acquaintances. (If you are a health care worker, please do NOT include any individuals you have given professional care to, we will ask about those contacts in a minute).

J31. How many people do you personally know who do NOT have AIDS, but have tested positive for HIV, the virus that causes AIDS? (Choose one)

- 0      0 (none)
- 1      1
- 2      2 to 4
- 3      5 or more
- 97     Don't Know
- 98     Refuse to Answer

J32. How many people do you personally know who currently have AIDS or have died of AIDS? (Choose one)

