- 0      0 (none)
- 1      1
- 2      2 to 4
- 3      5 or more
- 97     Don't Know
- 98     Refuse to Answer

J33. How many people do you personally know who have hepatitis? (Choose one)

- 0 0 (none)
- 1 1
- 2 2 to 4
- 3 5 or more
- 97 Don't Know
- 98 Refuse to Answer

J34. How many people do you personally know who have died of hepatitis? (Choose one)

- 0 0 (none)
- 1 1
- 2 2 to 4
- 3 5 or more
- 97 Don't Know
- 98 Refuse to Answer

J35. In the 6 months have you been in close contact with anybody who had Hepatitis (yellow jaundice), e.g. people you live or work with?

- 0 No
- 1 Yes
- 97 Don't Know
- 98 Refuse to Answer

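### Appendix 7 tells health care workers that contact with infected patients will be asked about next, but no later item asks it, and J35 blurs the same exclusion

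*Protocol*

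**What the plan says.** The block J31-J35 in Appendix 7, Section J, opens by saying that "we would like to know about any personal contact you have had with persons who have HIV or hepatitis". It then sets the scope: "In each question, please include only family members, personal friends or acquaintances". Health care workers get a further instruction: "please do NOT include any individuals you have given professional care to, we will ask about those contacts in a minute".

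J31-J34 count people personally known who have HIV, AIDS or hepatitis; J33, for example, asks "How many people do you personally know who have hepatitis". J35 asks whether, in the 6 months, "have you been in close contact with anybody who had Hepatitis (yellow jaundice), e.g. people you live or work with".

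Section K follows directly and has three items. K1 asks "Do you work where you are exposed to human bodily fluids (e.g. blood, urine, feces, saliva". K2 asks whether "in your professional work have you had a needle stick injury" in the 6 months before donation. K3 asks about blood, body fluids or excrement splashed into the eyes, mouth or broken skin. A No to K1 skips the rest of Section K.

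The Objective 1b hypotheses (Section 4) and the matching predictor list (Section 4.9) name personal contact with an HBV-infected person as one of three expected risk factors.

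**The concern.** The contacts that the preamble promises to return to can only be infected people whom the respondent looked after professionally, because the block is about contact with persons who have HIV or hepatitis. The instrument takes these contacts out of one set of items and never collects them in another. A questionnaire gap of this kind cannot be repaired at analysis.

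Two things are at stake. First, the study cannot estimate an association of incident HIV or HBV with caring for known infected patients, although the questionnaire tells respondents that it collects this. Second, J35 uses people at work as an example while the exclusion of patients still applies to it. Of two nurses with the same exposure, one may answer Yes and the other No. J35 is also the only recent-contact item for hepatitis in the block, so inconsistent coding there touches a named Objective 1b exposure.

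**Working it through.** The plan states no figure here, so the main check is a reading of the instrument against its own instruction.

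**Step 1. Is the promised item anywhere after the preamble?**
- J31-J35: patients are excluded by instruction.
- K1: work with exposure to body fluids. Infection status of the source not asked.
- K2: needle stick. Source status not asked.
- K3: splash. Source status not asked.
- L1-L9: the case's own infection, treatment and presumed route. Controls skip the section, so even the free-text items L2 and L9 give no case-control contrast.

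Result: 0 of 3 Section K items and none of the Section L items ask about professional contact with an infected person.

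**Step 2. Is it anywhere earlier?** B13b records occupation (code 4 is medical/healthcare). G7a and G7b ask about sex with someone whose job involves blood exposure. Neither asks about the respondent's own infected patients.

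**Step 3. What does a compliant respondent record?** A health worker whose only infected contacts are patients answers none on J31-J34 and No on J35. On these five items the record equals that of a donor with no contact. It differs from that donor's only through B13b and K1-K3.

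**Step 4. How much could this move the personal-contact odds ratio? (Illustrative.)** All inputs are assumptions, since the protocol gives none: 3-8% of donors are health workers and half cared for a known infected person, so professional contact is 1.5-4% of controls; personal contact is 10% of controls, with a true odds ratio of 3 and no overlap between the two. Let r be the professional-only share of controls, n the share with neither contact, and OR_p the odds ratio for professional contact. With professional contacts left in the reference group,

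observed OR = 3 / [(r × OR_p + n) / (r + n)].

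- r = 0.015, OR_p = 3: (0.045 + 0.885)/0.900 = 1.033; 3/1.033 = 2.90.
- r = 0.04, OR_p = 3: (0.12 + 0.86)/0.90 = 1.089; 3/1.089 = 2.76.
- OR_p = 1.5: 2.98 (r = 0.015) and 2.93 (r = 0.04).
- OR_p = 1: 3.00, no change.

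The largest change is 1 - 2.76/3 = 8%, and it needs professional contact to be as strong a risk factor as personal contact.

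**Step 5. Would the missing exposure be analysable if collected? (Illustrative.)** Take an odds ratio of 3, two-sided alpha 0.05, independent sampling, and the 150 cases and 450 controls of Table 9. Case exposure is p1 = 3p0/(1 - p0 + 3p0). Power uses the pooled-variance normal approximation for two proportions.

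| Control exposure p0 | Case exposure p1 | Power, 150 v 450 | Power, 150 v 900 |
|---|---|---|---|
| 0.015 | 0.044 | 0.53 | 0.62 |
| 0.025 | 0.071 | 0.70 | 0.77 |
| 0.040 | 0.111 | 0.85 | 0.90 |

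At p0 = 0.015 the expected exposed counts are only 150 × 0.0437 = 6.6 cases and 450 × 0.015 = 6.75 controls, so the approximation is rough and precision low. Section 4.8.1 says independence cannot be assumed, because controls are sampled within clinics; these figures ignore clustering.

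**The case against.** The strongest reply is that the exclusion is deliberate. Objective 1b is about personal contact, the block is introduced that way, and a nurse with no infected family or friends who answers none is coded correctly for that exposure. No hypothesis in Section 4 concerns occupational contact. Health workers are identifiable from B13b, and K1-K3 measure occupational body-fluid exposure, needle sticks and splashes. In J35, people one works with naturally means colleagues, so patients stay excluded. The instrument is also visibly unfinished: the OMB number is a placeholder and J14a carries a drafting query. On this view, deleting the promise is enough.

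Most of this stands, and it rules out two stronger readings. A reader might infer that the Objective 1b contact estimate is materially biased by health workers in the reference group. The documents do not support that: the hypothesis is limited to personal contact, the dilution in Step 4 is small and rests on assumed inputs, and the analyst can adjust for health workers or set them apart using B13b and K1. A reader might also infer that occupational exposure as a whole is lost. It is not; only contact with patients known to be infected, and the source's status, are missing.

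What the reply does not remove is the unmet promise and the ambiguity in J35. Reading work contacts as colleagues is plausible but not stated, and a self-administered interview should not leave the choice to the respondent.

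**Conclusion.** The point holds as an instrument defect of limited reach. The preamble promises a measurement that the questionnaire does not contain. As printed, professional contact with known HIV- or hepatitis-infected persons cannot be estimated, and J35 invites inconsistent answers from health workers. This part rests on the printed text alone.

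The personal-contact hypothesis of Objective 1b is not materially affected. The number of respondents concerned is unknown. The figures in Steps 4 and 5 depend on an assumed health-worker share, assumed odds ratios and independent sampling; they illustrate scale and carry no part of the conclusion. It is worth correcting because the correction is cheap and the data cannot be recovered once interviews are done.

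**What to change.** Before ACASI programming and OMB clearance (Section 4.6 says the instruments still need approval):

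1. Add to Section K, for anyone with K1 other than No or with B13b = 4: *In the 6 months before your donation, in your work, did you give care to anyone you knew to have (a) hepatitis B, (b) HIV?* Adjust the K1 skip so that a respondent with B13b = 4 and K1 = No still reaches the item.
2. State in J35 that patients are excluded, or delete the reference to people at work. The first option keeps infected colleagues reportable.
3. Analyse professional contact as its own exploratory exposure, separate from personal contact.

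If the items are not added, remove the promise from the preamble, still clarify J35, and state that professional contact with infected persons is not measured.

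The cost is two short answers, a skip change and one wording edit, with a few seconds of interview time for a small subgroup. The exposure is likely to be rare, so its estimate would probably be imprecise.

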***If Study Group 3 (A7=3), Skip to Instruction After L9.***

**SECTION L - EXPOSURE AND TREATMENT**

*Study Group 1 Only (A7=1)*

**READ and HEARD:** *This is the final section of the questionnaire. It may be difficult for you to respond to these questions. Again, the responses are anonymous and will help us improve blood safety in South Africa.*

L1. Did you know your HIV status before your donation? (Choose one)

- 0 No
- 1 Yes
- 97 Don't Know
- 98 Refuse to Answer

L2. How do you think you may have become infected with HIV?

-----

L3. When do you think you may have been infected with HIV? (Year)

- \_\_\_\_\_\_ YYYY
- 2097 Don't Know (Year)
- 2098 Refuse to Answer (Year)

L4. When do you think you may have been infected with HIV? (Month) (Choose one)

- January
- February
- March
- April
- May
- June
- July
- August
- September
- October
- November
- December
- Don't Know
- Refuse to Answer

L5. Are you currently taking antiretroviral medicines, also called ARVs? (Choose one)

- 0 No
- 1 Yes skip to L7?
- 97 Don't Know
- 98 Refuse to Answer

L6. Have you taken antiretrovirals (ARVs) in the past? (Choose one)

- 0 No
- 1 Yes
- 97 Don't Know
- 98 Refuse to Answer

L7. (Ask of Women Only) If Female: Did you know you were HIV-positive prior to or during your most recent pregnancy?

- 0 No
- 1 Yes
- 96 Not applicable, never been pregnant **SKIP to After L9.**
- 97 Don't Know
- 98 Refuse to Answer

L8. (Ask of Women Only) Did you take antiretrovirals during your most recent pregnancy to try to prevent HIV transmission to your baby?

- 0 No
- 1 Yes
- 96 Not Applicable
- 97 Don't Know
- 98 Refuse to Answer

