The significance of this study is related to its three objectives: One, determination of demographic and behavioural risk factors for incident HIV and HBV hold great promise for informing targeted prevention measures by blood banks and public health authorities. The potential for identifying persons who are recently infected with both HIV and HBV also exists. In countries where the two viruses are highly endemic the rate of co-infection can be as high as 25%. In recent years, approximately 2.4 % of those SANBS blood donors with confirmed HIV or HBV infection have been co-infected. Prospective collection of incidence data allows for measurement of secular trends and the methodological approaches of behavioural and molecular surveillance we will use may also be of value to other countries with generalized HIV and HBV epidemics in Africa and Asia. Two, we will determine the viral subtype and drug resistance profile of all recently acquired HIV infections, and the genotype of recently acquired HBV infections, allowing study of viral evolution, viral fitness and pathogenicity. While we expect few HIV-HBV co-infections, persons with co-infection are known to have up to five-fold faster disease progression and so efforts to understand the epidemiology of both HIV and HBV, among individuals who are co-infected within the SANBS donor population has the potential for direct impact on public health and health care services in South Africa. In addition for HIV we will be able to determine the frequency at which drug-resistant strains are being transmitted in the population which has clear implications for changing pharmacogenetics and appropriate antiretroviral medicines. Three, evaluation of donors with recently acquired HIV infection and “elite controllers” (HIV antibody positive, ID-NAT negative infections) at multiple time points will be valuable to virologists and immunologists studying the natural history of early HIV infection. These studies will be useful in identifying appropriate HIV drug therapy regimens for this context, as well as strategies for producing an effective HIV vaccine, which has eluded 30 years of HIV research.

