**SECTION C - PREVIOUS DONATION AND HIV TESTING**

C1. Before your recent donation, have you ever donated blood? (Choose one)

- 0 No **Skip to C4**
- 1 Yes
- 97 Don't Know
- 98 Refuse to Answer

C2. Before your recent donation, how many times have you donated blood? (Choose one)

- 1 1 time
- 2 2 or more times
- 97 Don't Know
- 98 Refuse to Answer

C3. At the time of your donation, were you given information about who should not donate blood?  
(Check all that apply)

- 0 No
- 1 Yes, written information (pamphlets)
- 2 Yes, through discussion with the donor staff at the donation centre
- 97 Don't Know
- 98 Refuse to Answer

C4. Do you know of places in your community where you can be tested free of charge for HIV?

- 0 No
- 1 Yes
- 97 Don't Know
- 98 Refuse to Answer

C5. Not including HIV testing conducted as part of blood donation, have you ever been tested for HIV?  
(Choose one)

- 0 No ***Skip to instruction before D1***
- 1 Yes
- 97 Don't Know
- 98 Refuse to Answer

C6. Not including HIV testing conducted as part of blood donation, how many times have you been tested for HIV? (Choose one)

- 0 Never
- 1 1 time
- 2 2 or more times
- 97 Don't Know
- 98 Refuse to Answer

C7a. Not including HIV testing done as part of blood donation, what was the primary reason for the most recent HIV test? (Choose one)

- 1 Pregnancy care
- 2 Health insurance

- 3 Doctor's order, routine medical care, hospitalisation or surgery
- 4 I wanted to know my HIV status
- 5 Other
- 97 Don't Know
- 98 Refuse to Answer

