***If F1a is equal to 1 and F1b is equal to 0, then skip to Section G.***

F12. What is partner 1's HIV status? (Choose one)

- 1 Positive
- 2 Negative
- 3 Unknown
- 98 Refuse to Answer

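### Questionnaire items L1 and L5–L6 do not record whether an HIV case knew of a positive result, or had taken ARVs, before the index donation

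*Protocol*

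**What the plan says.** Section L of the Appendix 7 questionnaire puts L1 to L8 to HIV cases only. L1 reads "Did you know your HIV status before your donation", answered No, Yes, Don't Know or Refuse. L5 reads "Are you currently taking antiretroviral medicines, also called ARVs". Its Yes option carries a note routing the respondent to L7, printed with a question mark. L6, which that route bypasses, reads "Have you taken antiretrovirals (ARVs) in the past". Women are then asked "Did you know you were HIV-positive prior to or during your most recent pregnancy" and "Did you take antiretrovirals during your most recent pregnancy to try to prevent HIV transmission to your baby".

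Section 4.4.1 says the questionnaire measures exposure over two windows, lifetime and the half-year before the index donation. Section 4.2.2 (Participant Enrollment) places the interview after recall, normally at the retest visit but with the option of a later date, and says that confirmed cases will be encouraged to obtain medical care.

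On use of the results, Section 3 says the study will be able to "determine the frequency at which drug-resistant strains are being transmitted in the population". Objective 2a and Section 4.9 take drug resistance in incident HIV cases as a binary outcome. Table 1 and Section 4.4.1 have resistance determined on index-donation plasma, with a follow-up sample only when no index sample is available.

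**The concern.** Two things are not pinned down.

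The first is which status L1 refers to. Elsewhere in the same instrument the term covers either result. F12 asks "What is partner 1's HIV status" and offers positive, negative and unknown. C7a lists "I wanted to know my HIV status" as a reason for any test. A Yes to L1 can therefore mean that the donor knew of the infection or believed there was none.

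The second is when ARVs were taken relative to the donation. Because the resistance result comes mainly from index plasma, the relevant exposure is ARV use before that donation. L5 is anchored to the interview and L6 to an unspecified past. Resistance in a donor with earlier treatment may have been acquired on treatment, and counting it as transmitted would blur what Section 3 wants to learn. A variable that the interview does not collect cannot be supplied later by an analysis plan.

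**Working it through.** No formula applies. The check is to follow each answer path and then look for any other item that closes the gap.

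**Answer paths for an HIV case**

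| Path | What the record shows | What it leaves open |
|---|---|---|
| L1 = Yes | The donor believed they knew a result before donating | Whether that result was positive or negative |
| L5 = Yes (L6 bypassed) | On ARVs at the interview | Whether they began before or after the index donation |
| L5 = No, L6 = Yes | ARVs at some past time | When, relative to the donation |
| L5 = No, L6 = No | Self-reported ARV-naive | Nothing material for transmitted resistance |
| L7 or L8 = Yes (women who have been pregnant) | Known positive, or on ARVs, around the latest pregnancy | When that pregnancy was, relative to the donation |

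**Other items that might help**

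- Section C asks whether, how often, why and where the donor was tested, but never the result.
- L2 to L4 ask how and when the donor thinks infection occurred. That is a perceived date of infection, not a date of diagnosis.
- Appendix 8, item B4, asks about starting ARVs, but only of Objective 3 participants and only since the last study visit.

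None of these dates a known positive result or ARV use against the index donation. For men and for women who have never been pregnant, no later coded item resolves L1.

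**Where the gap can matter**

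Section 4.8.1 gives about 50 NAT-only infections and about 160 further LAg-recent infections a year:

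- total: 50 + 160 = 210
- NAT-only: 50 / 210 = 24%
- LAg-recent: 160 / 210 = 76%

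NAT-only cases are antibody-negative, and Section 3 puts antibody detection at about 21 days, so treatment before donation is unlikely in them. That leaves mainly the LAg-recent group. The 76% is the share of identified infections in which the question is open. It carries over to enrolled cases only if both groups enrol at similar rates, and it says nothing about how many were treated.

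**What cannot be computed**

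The documents give no figure for the share of cases diagnosed or treated before donation, the share starting ARVs between donation and interview, or the share who would read L1 as covering a negative result. Any size for the effect would rest on invented inputs, so none is given.

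**The case against.** The strongest reply has four parts.

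- **Timing.** Most interviews take place at the return visit. NAT-yield donors give samples, consent and complete the interview before confirmatory results are final, and concordant cases are counselled and enrolled when they return. Starting ARVs in the gap needs a delayed interview or care obtained elsewhere. This stands, and it limits how often L5 = Yes is uninterpretable.
- **Existing items.** Restricting Objective 2a to L5 = No with L6 = No gives a self-reported ARV-naive group without any new question. This also stands. The cost is that donors who started after donation are dropped, as are donors whose undated past use cannot be placed.
- **Context of L1.** It is shown only to HIV cases and directly precedes questions on how and when they became infected, so many may read it as asking about a positive status. That is plausible, but it makes the item ambiguous rather than clear.
- **Draft status.** The question mark on the L5 routing is a drafting note, and Section 4.11 schedules development and pilot testing of the interview. That is a reason to settle the routing before fielding, not to leave it.

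A reader might infer that L1 will be reported as the share of cases who knowingly donated while infected, and that this share will be badly inflated. The documents do not support that. No objective names such an estimate, Section 4.9 does not mention L1, and nothing shows how respondents would read it.

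**Conclusion.** The ambiguity in L1 and the missing anchor in L5 and L6 are plain from the printed text, and no other item closes the gap. For L5 = Yes, the interview as written does not show whether ARVs preceded the donation.

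The consequence for Objective 2a is probably small and lies mainly in LAg-recent cases. That rests on two points: treatment before donation is unlikely in antibody-negative cases, and the ARV-naive group can already be identified by self-report. A reader might go further and infer that the interview cannot support a transmitted-resistance analysis at all, or that the resistance proportion will be materially biased. Neither follows: the ARV-naive pattern supports such an analysis, and the documents contain no figures from which a bias could be derived.

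No power calculation and no Objective 1 hypothesis depends on these items. The point is a worthwhile improvement to the instrument, not a threat to the study.

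**What to change.** 1. Reword L1 to ask whether, before that donation, the donor had ever been told that they were HIV-positive.
2. Anchor L5 to the donation: was the donor taking ARVs at that time?
3. Remove the skip from L5 and ask every HIV case L6 in the form: had the donor ever taken ARVs before that donation?
4. Add a separate item for ARVs started since the donation. It also covers cases whose resistance result comes from a follow-up sample.
5. Add one sentence to Section 4.9 under Objective 2a: transmitted resistance is reported in donors with no ARV use before donation, and the remaining donors are shown separately.

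The cost is rewording the existing items, adding one, one routing change made before the interview is programmed, and slightly more interview time. A few cases may leave the transmitted-resistance denominator.
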